### **F.1.2. Per-Protocol**

Sensitivity analyses will include a per-protocol approach in which we may control for the level of adherence (see §D.12.1) to study arm protocols and/or exclude non-adherent entities from analyses.

### **F.1.3. As-Treated**

Sensitivity analyses will include an as-treated approach in which we investigate the effect of increased wellness activities/resources (see §D.12.1) on patient and resident outcomes, regardless of study arm assignment.

## **F.2. DESCRIPTIVE STATISTICS**

There remains controversy regarding the appropriateness of statistical testing to evaluate balance of baseline characteristics across study arms following randomization. In accordance with CONSORT 2010 guidelines, we will assess baseline characteristics of programs and residents across both study arms, but we will refrain from statistical testing for differences across arms, because any differences across study arms will be known to have been due to chance.

## F.3. STATISTICAL EVALUATION PLAN

### F.3.1. Analysis of Primary Outcome

The primary study hypothesis is that:

- Residents in programs randomized to Intervention will have lower mean burnout scores compared to residents in programs randomized to Control

#### F.3.1.1. Unadjusted Analyses

Under randomization of programs to treatment arms, treatment should be orthogonal to observed and unobserved confounders. An unadjusted comparison of mean burnout scores across study arms would provide an intent-to-treat estimate of the effect of study assignment on resident burnout. We may carry this out using a cluster-corrected Student's t-test to compare mean burnout scores across study arms, and/or we may estimate a simple hierarchical linear regression of the form

$$y_{ij} = \alpha_0 + \beta_0 TREAT_j + \gamma_1 Q_{2j} + \gamma_2 Q_{3j} + \gamma_3 Q_{4j} + \gamma_4 Q_{5j} + \zeta_j + \epsilon_{ij}$$

where  $y_{ij}$  is the burnout T-score of resident  $i$  in program  $j$ ,  $TREAT_j$  is the study arm assignment of program  $j$ , and  $Q_{2j}$ - $Q_{5j}$  are dummy variables indicating program  $j$ 's randomization stratum (program quartile ranking based on 2019 ABSITE burnout scores, plus a fifth stratum for programs with no 2019 ABSITE data). In this model, under randomization of programs to study arms, the coefficient  $\beta_0$  is the unadjusted population-averaged intent-to-treat estimate of the effect of assignment to intervention on mean resident burnout. Other parameters in the model are the constant ( $\alpha_0$ ), coefficients on program-level randomization strata ( $\gamma_1$ - $\gamma_m$ ), program-level random intercepts ( $\zeta_j$ ) and individual-level errors ( $\epsilon_{ij}$ ).

#### F.3.1.2. Adjusted Analyses

Covariate adjustment in evaluations of randomized trials is generally done for purposes of increasing statistical efficiency by reducing variance within treatment groups. Covariate adjustment is also sometimes also undertaken on the basis of chance imbalance of baseline characteristics between study groups. Although programs will be randomized to treatment arms in this study, we anticipate considerable variation in the number of ABSITE respondents per program. In the 2019 ABSITE data, the average program had 23 resident respondents (mean=23.11, SD=11.15; coefficient of variation=48%), but the range spanned from a minimum of 3 residents per program to a maximum of 59 residents per program. Such dispersion in cluster sizes may lead to imbalance of resident characteristics

Thus, our analytic approach to evaluating our primary hypothesis will be to estimate a 2-level hierarchical linear model of the general form:

$$y_{ij} = \alpha_0 + \beta_0 TREAT_j + \beta_1 x_{1ij} + \beta_2 x_{2ij} + \cdots + \beta_k x_{kij} + \gamma_1 z_{1j} + \cdots + \gamma_m z_{mj} + \zeta_j + \epsilon_{ij}$$

where  $y_{ij}$  is the burnout T-score of resident  $i$  in program  $j$ ,  $TREAT_j$  is the study arm assignment of program  $j$ , and  $x_{1ij}$ - $x_{kij}$  are resident-level covariates and  $z_{1j}$ - $z_{mj}$  are program-level covariates to be adjusted for, including sampling stratification variables. In this model, under randomization of programs to study arms, the coefficient  $\beta_0$  is the adjusted population-averaged intent-to-treat estimate of the effect of assignment to intervention on mean resident burnout. A coefficient  $\beta_0 < 0$  that is statistically

significant with a one-tailed  $p<0.0443$  provides evidence supporting the effectiveness of the intervention over usual care. Other parameters in the model are the constant ( $\alpha_0$ ), coefficients on other resident-level covariates ( $\beta_1-\beta_k$ ), coefficients on program-level covariates ( $\gamma_1-\gamma_m$ ), program-level random intercepts ( $\zeta_j$ ) and individual-level errors ( $\epsilon_{ij}$ ).

Covariates may include variables listed in §E.3.: resident gender; resident relationship status; resident race; program type; program size; and randomization variables such as the quartile of program  $j$  ranked by 2019 program-level mean burnout scores. This list of covariates is subject to change.

Covariates will not include any other resident-level outcome or behavioral variable(s) that may be affected by the intervention as doing so may introduce endogeneity. Thus, for example, measures of career satisfaction, duty hour adherence, mistreatment, discrimination/harassment etc. will not be considered as controls in the evaluation of burnout.

Any structural measures – i.e., measures of program characteristics, policy, and/or programs related to burnout will not be controlled for in the primary analysis as doing so might over-control and attenuate the intent-to-treat estimate of the treatment assignment effect.

We will examine the mean, median, skewness and kurtosis values of the dependent variable to assess the normality of the dependent variable. If there is evidence of non-normality in the dependent variable, we may consider an appropriate transformation of the dependent variable; however, generalized linear mixed models are flexible and can accommodate alternative distributional assumptions regarding  $y_{ij}$  without altering the original scale of  $y_{ij}$ .

In accordance with the decision of the Principal Investigators, estimates from the adjusted analyses of the primary outcome will be reported as the primary findings of this study, although both adjusted and unadjusted analyses will be conducted.

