Using the constant estimated from the adjusted model as an estimate of the mean burnout score in Control (45.933) and the standard deviation of the Level-1 error component as the estimate of the standard deviation (9.027) around mean burnout scores in Control and assuming  $\alpha_{final}=0.0443$  for the final analysis, 80% power and  $ICC=0.012$ , we computed minimal detectable differences for a variety of hypothetical sample sizes, as reported in EXHIBIT D.8-B.

The scenario yielding the smallest detectable difference in adjusted mean burnout scores would be one in which there are 300 programs total, 150 programs in each arm with a mean of 25 residents per program. In this scenario, given our assumptions, we expect to be powered at 80% to detect a relative difference in mean burnout scores of -1.46%.

In a conservative scenario with 100 programs randomized to each study arm (200 programs total) and an average of 15 residents per program, we expect to be powered at 80% to detect a relative difference in mean burnout scores of -2.22%.

In a moderate scenario with 110 programs randomized to each study arm (220 programs total) and an average of 20 residents per program, we expect to be powered at 80% to detect a relative difference in mean burnout scores of -1.87%.

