#### EXHIBIT D.8.B Minimal Detectable Differences for Primary Analysis under Varying Sample Size Scenarios

Number of Programs (Clusters) per Arm	Number of Residents per	Usual Care Mean Burnout	Estimated Intervention	Minimal Detectable Difference	Relative Difference (%)

	Program (Mean Cluster Size)		Mean Burnout		
150	25	45.93	45.26	-0.67	-1.46%
150	20	45.93	45.19	-0.74	-1.61%
150	15	45.93	45.10	-0.83	-1.81%
125	25	45.93	45.19	-0.74	-1.61%
125	20	45.93	45.12	-0.81	-1.76%
125	15	45.93	45.02	-0.91	-1.98%
110	25	45.93	45.14	-0.79	-1.72%
110	20	45.93	45.07	-0.86	-1.87%
110	15	45.93	44.96	-0.97	-2.11%
100	25	45.93	45.10	-0.83	-1.81%
100	20	45.93	45.03	-0.90	-1.96%
100	15	45.93	44.91	-1.02	-2.22%

NOTES: Minimal detectable difference from adjusted estimate of mean burnout scores, assuming mean burnout T-scores in Usual Care=45.933, SD in both arms=9.027, ICC=0.012, alphafinal=0.0443 and power=80%, based on preliminary estimates in EXHIBIT D.8-B. Relative difference is expressed as a percent of Usual Care mean.

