### **D.12.2. Data Safety Monitoring**

#### **D.12.2.1. Data Safety Monitoring Board (DSMB)**

We convened a Data Safety Monitoring Board (DSMB) to independently review study progress at regular intervals. The purpose for establishing a DSMB is to serve as an independent review body to evaluate the results of a planned Interim Analysis that is scheduled for January 2021. The Interim Analysis, described in greater detail in §F.8, will use SECOND Trial Resident Survey data collected from participating programs from 2019 to 2021 to compare resident burnout in programs randomized to Intervention vs. those in programs randomized to Control. The DSMB was charged with determining whether early stopping rules for the SECOND Trial had been met, and if so, to terminate the trial out of consideration for resident wellness.

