##### ***F.3.4.4. Multiple Comparisons***

In the evaluation of secondary outcomes, we anticipate multiple comparisons within a family of outcomes where we consider families of outcomes to be groups of similar outcome measures within a domain (e.g.

resident education outcomes). To control for familywise error rate in conducting multiple hypothesis tests, we will adjust the overall study p-value ( $p=0.0444$ , see §F.4) using the Bonferroni correction.

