#### **F.4. STATISTICAL SIGNIFICANCE LEVEL**

The overall level of statistical significance for this study will be set at  $p<0.05$ . One interim analysis is planned for the midpoint of this study. Assuming an O'Brien-Fleming alpha-spending function, the overall  $\alpha=0.05$  will be adjusted (LANDEMTS, Stata module) to  $\alpha_{\text{interim}}=0.0056$  for the interim analysis and  $\alpha_{\text{final}}=0.0444$  for the final analysis.

In analyses where there are multiple comparisons – for example, as in the case of multiple tests of a single hypothesis using different indicators for the same underlying construct in separate models, p-values will be adjusted using Bonferroni's method or another similar method to control for the family-wise error rate.

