## **F.5. PLANNED INTERIM ANALYSIS**

### **F.5.1. Interim Analysis Overview**

A planned Interim Analysis will be undertaken at the midpoint of the Study Period. The purpose of the Interim Analysis is to assess whether there are any excess resident safety/wellness risks with respect to burnout that would raise ethical concerns about trial continuation.

The Interim Analysis will assess whether there are statistically significant differences in resident burnout scores across study arms (§F.3.1.2).

Results of the Interim Analysis will be reported to the DSMB (§D.12). Based on results of the Interim Analysis, the DSMB is charged with deciding whether the Trial should be terminated early or if the Trial can continue per protocol. Results of the Interim Analysis will not be used to modify Trial design or protocol.

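### The detectable differences in Exhibit D.8.B come from a two-sided test, but the primary decision rule is one-tailed, and the plan never states the sidedness of the overall or interim levels

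*SAP*

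**What the plan says.** The primary hypothesis in F.3.1 is directional: Intervention residents "will have lower mean burnout scores compared to residents in programs randomized to Control". F.3.1.2 follows it, counting a negative coefficient as evidence of effectiveness if it is "significant with a one-tailed" p<0.0443.

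The note to Exhibit D.8.B gives the power inputs as "assuming mean burnout T-scores in Usual Care=45.933, SD in both arms=9.027, ICC=0.012", with a final alpha of 0.0443 and 80% power. It does not mention sidedness. D.8.3 draws its statements from that exhibit. For 110 programs per arm and 20 residents per program it says "we expect to be powered at 80% to detect a relative difference in mean burnout scores of -1.87" per cent.

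F.4 opens with "The overall level of statistical significance for this study will be set at" p<0.05 and splits this into 0.0056 (interim) and 0.0444 (final) by O'Brien-Fleming spending, again without sidedness. F.3.4.4, where "we will adjust the overall study p-value" is the instruction for secondary outcomes, also uses 0.0444.

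D.12.2.1 describes the interim as a look "to compare resident burnout in programs randomized to Intervention vs. those in programs randomized to Control", with no direction. F.5.1 gives its purpose as "to assess whether there are any excess resident safety/wellness risks with respect to burnout that would raise ethical concerns about trial continuation" and cites F.3.1.2 for the comparison. F.5.3 makes a statistically significant difference between arms a required condition for early termination, alongside a judgement by the DSMB that the difference matters for residents, whether as a gain or a loss. F.5.4 refers to F.3.1 for methods and sets 0.0056.

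**The concern.** A power statement should describe the test that decides the trial. If the exhibit was computed for a two-sided test and the decision rule is one-tailed, the printed 80% and the printed detectable differences belong to a stricter test than the one to be run. With no sidedness in F.4, a reader cannot tell from the text which design the overall 5% refers to.

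The interim look has a related gap. Its declared purpose is to find harm, but the section it cites contains only a rule for benefit. If that rule is carried over, higher burnout in the Intervention arm could never be statistically significant, and the first condition in F.5.3 could not be met in the direction the look exists to detect. The DSMB should not have to choose the reading after seeing the data.

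**Working it through.** **Inputs** (Exhibit D.8.B): SD 9.027, ICC 0.012, final alpha 0.0443, power 80% (z = 0.8416), control mean 45.933; k programs per arm, m residents per program.

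**Formula.** SE = 9.027 × √[2(1 + (m−1)×0.012)/(k×m)]; detectable difference = (z_alpha + 0.8416) × SE. For alpha 0.0443, z_alpha is 2.0112 two-sided and 1.7028 one-tailed.

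**Moderate scenario, 110 × 20.** SE = 9.027 × √(2 × 1.228/2200) = 0.3016.
- Two-sided: (2.0112 + 0.8416) × 0.3016 = 0.860. Printed: 0.86.
- One-tailed: (1.7028 + 0.8416) × 0.3016 = 0.767.

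**All rows** (absolute values):

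| Programs per arm × residents | Printed | Two-sided 0.0443 | One-tailed 0.0443 |
|---|---|---|---|
| 150 × 25 | 0.67 | 0.675 | 0.602 |
| 150 × 20 | 0.74 | 0.737 | 0.657 |
| 150 × 15 | 0.83 | 0.830 | 0.740 |
| 125 × 25 | 0.74 | 0.739 | 0.659 |
| 125 × 20 | 0.81 | 0.807 | 0.720 |
| 125 × 15 | 0.91 | 0.909 | 0.811 |
| 110 × 25 | 0.79 | 0.788 | 0.703 |
| 110 × 20 | 0.86 | 0.860 | 0.767 |
| 110 × 15 | 0.97 | 0.969 | 0.864 |
| 100 × 25 | 0.83 | 0.827 | 0.737 |
| 100 × 20 | 0.90 | 0.902 | 0.805 |
| 100 × 15 | 1.02 | 1.016 | 0.906 |

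The two-sided column matches every row to within 0.005; the one-tailed column matches none. Using 0.0444 instead of 0.0443 moves no row by more than 0.0004, so the table cannot show which of the two levels was used.

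**Power at the printed differences under the one-tailed rule.** Φ(difference/SE − 1.7028). For 110 × 20: Φ(0.86/0.3016 − 1.7028) = 0.875. Over the 12 rows: 0.871 to 0.877.

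**D.8.3 percentages under the one-tailed rule.** 0.602/45.933 = 1.3% (printed 1.46%); 0.767/45.933 = 1.7% (printed 1.87%); 0.906/45.933 = 2.0% (printed 2.22%).

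**Enrolled sample.** For 106 and 103 programs (Exhibit D.9), assuming 20 respondents per program, SE = 9.027 × √[(1.228/20)(1/106 + 1/103)] = 0.3095. The detectable difference is 0.88 two-sided and 0.79 one-tailed.

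**What the F.4 interim level suggests.** Assuming half the information at the interim, the O'Brien-Fleming-type spending function for one-sided 0.05 gives 2 − 2Φ(1.960/√0.5) = 0.0056, the printed value. A symmetric two-sided design with 0.025 per side gives 0.0031. The interim level thus points to one-sided 0.05, while the exhibit points to a two-sided test.

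**Overall error**, bivariate normal with correlation √0.5 (half information):
- both looks one-sided (0.0056, 0.0443): 0.0462
- both looks two-sided: 0.0466
- two-sided 0.0056 interim with one-tailed 0.0443 final: 0.0478 for any false rejection, 0.0450 for a false claim of benefit

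For the last combination, 0.0056 + 0.0443 = 0.0499 is an upper bound at any information fraction.

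**Interim cut-offs if 0.0056 is two-sided (z = 2.770).** The interim information is assumed to lie between all and half of that in D.8. For 110 × 20 the cut-off is 2.770 × 0.3016 = 0.84 points at full information and 2.770 × 0.4265 = 1.18 at half. With one-sided 0.0056 (z = 2.536) the cut-offs are 0.77 and 1.08. For a true excess of 1.0 point, a value assumed here for scale, the chance of reaching two-sided significance is Φ(1.0/SE − 2.770): 71% at full and 34% at half information. For 106/103 with 20 respondents the cut-offs are 0.86 and 1.21 and the chances 68% and 31%.

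**The case against.** The strongest reply is that nothing is lost. The one-tailed rule is declared in advance and fits the hypothesis, the power under it exceeds the stated 80%, and enrolment has closed at 209 programs, so the exhibit no longer guides recruitment. This stands as to consequence: there is neither low power nor inflated error. It does not make the printed figures right for the stated test.

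On the interim, the wording in D.12.2.1, F.5.1 and F.5.3 is non-directional, and the one-tailed sentence in F.3.1.2 is a criterion for effectiveness tied to the final level. The two-directional reading is therefore the better one. That also stands, but the plan does not state it, and F.5.1 cites the very section that holds the one-tailed rule.

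Third, 0.0056 agrees with one-sided 0.05 spending, so the exhibit may simply be the outlier, and a separately stated harm threshold would also close the interim gap. Both are fair. The first favours keeping the one-tailed rule and restating the table. The second means that calling 0.0056 two-sided is one acceptable solution, not the only one.

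**Conclusion.** The point holds and should be fixed, though it does not threaten the validity of the trial. The exhibit and the D.8.3 statements describe a two-sided test, while F.3.1.2 decides the trial on a one-tailed one. The printed differences overstate the 80% detectable difference by about 0.07 to 0.11 points, which is the same as understating power by about 7 to 8 percentage points. That the exhibit is two-sided is inferred from the reproduction, since the document does not say so, but the fit leaves no real doubt. These results take the plan's SD, ICC and equal cluster sizes as given; the overall error figures also assume half information at the interim, except for the 0.0499 bound.

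The discrepancy between 0.0443 and 0.0444 is numerically negligible and needs only consistency. The interim question is one of clarity: the likelier reading protects residents in both directions, but it should be written down before interim data are seen.

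**What to change.** 1. In F.4, state once whether 0.05, 0.0056 and the final level are one- or two-sided. Use a single final level in D.8, F.3.1.2, F.3.4.4 and F.4.
2. Make Exhibit D.8.B, D.8.3 and the primary rule refer to the same test, in one of two ways:
   - Keep the one-tailed rule and restate the exhibit. At one-tailed 0.0443, for 25/20/15 residents: 150 programs 0.60/0.66/0.74; 125 programs 0.66/0.72/0.81; 110 programs 0.70/0.77/0.86; 100 programs 0.74/0.80/0.91. The D.8.3 percentages become about −1.3%, −1.7% and −2.0%.
   - Or, at the sponsor's option, make the final test two-sided at 0.0443. The exhibit then stands as printed and only needs a label.
3. In F.5.4, state that the interim comparison at 0.0056 is two-sided, so that a difference in either direction can meet the first condition of F.5.3.

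**Cost.** Wording and at most one recomputed table; no new data, and no change of level beyond choosing 0.0443 or 0.0444. With the two-sided final test, power at 0.86 points (110 × 20) falls from about 87.5% to the 80% already stated. A two-sided interim raises the interim cut-off for benefit relative to a one-sided 0.0056: for 110 × 20, from 0.77 to 0.84 points at full D.8 information and from 1.08 to 1.18 at half.

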### **D.7.2. Definition of Randomization Strata**

Using data from the 2019 ABSITE Survey, we will compute mean resident burnout scores (§C.2) within each residency program. Programs will then be stratified into quartiles based on mean resident burnout scores in 2019. Programs that do not have 2019 ABSITE data will be grouped into a fifth stratum (“no previous data”).

The choice to define randomization strata on the basis of prior levels of resident burnout in programs was motivated by a desire to balance programs across study arms according to previous exposure to wellness activities and programming. We assume that extant levels of program engagement in issues of resident wellness will be reflected – at least to some degree – in mean levels of burnout within programs.

The number of strata was chosen based on a consideration of: avoiding thin strata; avoiding the inclusion of an excessive number of additional parameters in the final analytic models; and the ability to reduce between-program variance. Quartiles were chosen over tertiles because inclusion of quartiles in preliminary models showed that quartiles were slightly more effective in reducing between-program variance by (86% vs. 75%) compared to empty models (§D.8).

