### **D.7.3. Randomization Procedure and Treatment Assignment**

General surgery residency programs that enroll in the SECOND Trial will be grouped into four strata:

- Stratum 1 – Quartile 1, 2019 ABSITE program mean resident burnout scores
- Stratum 2 – Quartile 2, 2019 ABSITE program mean resident burnout scores
- Stratum 3 – Quartile 3, 2019 ABSITE program mean resident burnout scores
- Stratum 4 – Quartile 4, 2019 ABSITE program mean resident burnout scores
- Stratum 5 – *No data* on 2019 ABSITE program mean resident burnout score

Residency programs within each stratum will be assigned a unique, randomly-generated integer using a random-number generator. Residency programs within each stratum will be ordered in ascending order according to their randomly-assigned number. Four separate, blinded lists will be constructed containing the randomly-generated numbers corresponding to each program within each of the four strata. These blinded lists will be given to the Project Coordinator, who, with another Study Team member to be appointed, will alternately assign programs to Control or to Intervention. They will decide to start with control or intervention on the basis of a coin toss. An observer unaffiliated with the study will be present.

Once study arm assignments have been made for each of the four blinded lists, the blinded lists will then be sent back to the Statistical Analyst who will then unblind the lists. Final, unblinded residency program study arm assignments will be sent back to the Project Coordinator, so that participating programs may be notified of their study arm assignment. Study arm assignments will not be made public, but programs participating in the trial will be listed on the SECOND Trial website and [www.clinicaltrials.gov](http://www.clinicaltrials.gov).

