**EXHIBIT D.8.A. Preliminary Burnout Model for Power Calculations**

		Coefficient (95% CI)	
	Empty Model	Unadjusted Model	Adjusted Model
Program Strata (ref: Stratum 1)			
Stratum 2	---	2.510 (1.643-3.377)	2.134 (1.261-3.007)
Stratum 3	---	3.442 (2.575-4.309)	3.076 (2.202-3.951)
Stratum 4	---	6.258 (5.384-7.131)	5.598 (4.719-6.477)
Stratum 5	---	0.273 (-0.885-1.430)	---
Female (ref: male)	---	---	2.064 (1.544-2.583)
PGY level (ref: PGY1)			
PGY2	---	---	0.479 (-0.276-1.233)
PGY3	---	---	-0.101 (-0.874-0.673)
PGY4	---	---	-0.607 (-1.393-0.179)
PGY5	---	---	-0.548 (-1.350-0.253)
Relationship status (ref: not in relationship)			
Married	---	---	0.265 (-0.408-0.938)
In a relationship	---	---	0.965 (0.279-1.651)
Divorced/widowed	---	---	-0.318 (-2.203-1.566)
Non-white (ref: white)	---	---	-1.512 (-2.056- -0.968)
Geographic region (ref: Northeast)			
Southeast	---	---	0.124 (-0.690-0.939)
Midwest	---	---	0.307 (-0.484-1.098)
Southwest	---	---	0.033 (-0.958-1.023)
West	---	---	0.064 (-0.299-1.582)
Program type			
Community	---	---	-0.069 (-0.810-0.672)
Military	---	---	-0.322 (-1.985-1.341)
Program size	---	---	0.125 (-0.056-0.306)
Constant	49.753 (49.356-50.150)	46.970 (46.325-47.615)	45.933 (44.461-47.405)
Variance components			
Level-2	7.413 (5.627-9.767)	1.821 (1.010-3.285)	1.010 (0.417-2.446)
Level-1	83.483 (80.459-86.622)	83.721 (80.686-86.870)	81.485 (78.303-84.795)
Intraclass correlation	0.082	0.021	0.012
N residents	5962	5962	5075
N programs	300	300	237
Likelihood ratio test vs. linear model (x2)	172.20	18.29	6.94
P value	P<0.001	P<0.001	P=0.004

Data: 2019 (version 2) and 2018 ABSITE Survey data. The dependent variable is an IRT-derived burnout T-score based on 6 survey items corresponding to emotional exhaustion and depersonalization subscales (2019 ABSITE survey items Q15A-Q15F, see §E.1 for details). Program strata refers to program quartile based on program mean 2018 ABSITE burnout T-scores. The 5th stratum contains programs that had missing 2018 ABSITE data and were thus not ranked in a quartile. However, this stratum dropped out of the adjusted model due to collinearity.

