#### ***F.3.1.3. Program-Level Analyses***

To assess the robustness of our findings across alternative modeling approaches, we will also evaluate the effect of assignment to Intervention on aggregate, program-level mean burnout T-scores. For these analyses, we will construct mean burnout T-scores for each program in the study. We will then regress mean program burnout T-scores on a dichotomous variable indicating study arm assignment, as well as randomization strata as follows:

$$\text{MeanBurnout}_j = \alpha + \beta_0 \text{TREAT}_j + \gamma_1 Q_{2j} + \gamma_2 Q_{3j} + \gamma_3 Q_{4j} + \nu_j$$

where  $\text{MeanBurnout}_j$  is the mean burnout score in program  $j$ ,  $\text{TREAT}_j$  is the study arm assignment of program  $j$ , and  $Q_{2j} - Q_{4j}$  are randomization strata (assuming quartiles of previous year's mean burnout scores are used for stratification, with  $Q_{1j}$  omitted as the reference category). Here,  $\beta_0$  is the intent-to-treat estimate of the effect of assignment to Intervention on mean program burnout rates, and we hypothesize  $\beta_0 < 0$ .

We may additionally estimate adjusted program-level regressions by incorporating program-level covariates into the model above.

We anticipate estimating this program-level model using ordinary least squares (OLS) regression, pending assessment of program-level mean burnout T-scores for normality. In the 2019 ABSITE data,

program-mean burnout T-scores had a skewness of -0.558 and kurtosis of 3.587. Shapiro-Wilk, Shapiro-Francia, and skewness-kurtosis tests for normality were significant. Decisions regarding modeling and transformation of the dependent variable will depend on the normality of program-level mean burnout scores in the actual study data, as well as considerations of statistical assumptions and interpretability of results.

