#### **F.3.3.1. Pre-Post with Control Analyses**

As an additional perspective, we may explore analyses that take baseline rates of programs in each arm into account. In these analyses, rather than identifying the intervention on the basis of a post-only comparison between Intervention and Control, we examine whether *improvement* in outcomes was greater among programs randomized to Intervention relative to improvement in outcomes among programs randomized to Control. These analyses may be executed by regressing pre-post differences in outcomes on study arm assignment and controls for sampling strata as well as other covariates at the discretion of Investigators and analysts, as appropriate to the data. We do not take this approach as our main analytic strategy because the Intervention under investigation is largely untested. Prospective power calculations would require two assumptions: (a) the rate of secular improvement in the absence of the intervention; and (b) the effectiveness of the intervention or its components to estimate the expected difference in mean rates within the Intervention group.

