### **F.5.2. Schedule of Interim Analysis**

The planned Interim Analysis is scheduled for April 2021. This is approximately midpoint through the SECOND Trial Study period, as the first SECOND Trial Resident Survey after dissemination of the Intervention will occur in January 2021.

ACS NSQIP data for the subset of SECOND sites that participate is scheduled to be delivered to the Study Team in January 2021. Because of ACS NSQIP data collection procedures which allow participating hospitals 120 days after the date of a procedure to complete data collection and entry.

A confidential Interim Report will be circulated to DSMB members in May 2021. A DSMB conference call is scheduled for May 2021.

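### The primary-outcome models use 2019 program burnout only as randomization strata; adding the continuous 2019 program mean would be a nearly free improvement, and Exhibit D.9 needs reconciling

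*SAP*

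**What the plan says.** D.7.2 states that, from the 2019 survey, "we will compute mean resident burnout scores (§C.2) within each residency program". The scores are cut into quartiles, and programs without 2019 data form a fifth stratum. D.7.3 orders programs at random within each stratum; study staff "will alternately assign programs to Control or to Intervention".

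The three primary-outcome models then treat baseline burnout as follows:

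- **F.3.1.1 (unadjusted):** stratum dummies Q2 to Q5, defined as "program quartile ranking based on 2019 ABSITE burnout scores, plus a fifth stratum for programs with no 2019 ABSITE data".
- **F.3.1.2 (adjusted, reported as the primary finding):** program-level covariates include the stratification variables. The list of possible covariates ends with the quartile "ranked by 2019 program-level mean burnout scores. This list of covariates is subject to change".
- **F.3.1.3 (program-level):** "We will then regress mean program burnout T-scores on a dichotomous variable indicating study arm assignment, as well as randomization strata as follows". The formula that follows has Q2 to Q4 only and no term for the fifth stratum.

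Baseline outcome data appear once more, in F.3.3.1: "As an additional perspective, we may explore analyses that take baseline rates of programs in each arm into account". That analysis uses pre-post differences, is optional, and is expressly not the main strategy.

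Exhibit D.9 gives 2019 mean T-scores of 50.48 (SD 3.07) for 106 Control programs and 49.98 (SD 3.88) for 103 Intervention programs.

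**The concern.** F.3.1.2 justifies covariate adjustment by efficiency and by chance imbalance at baseline. The baseline value of the primary outcome is the natural candidate on both counts, and the trial already holds it in continuous form. Quartile dummies discard its variation inside each quartile. If the arms differ there, no named model corrects for it. Because the covariate list is open, the choice between quartile and continuous score could also be made after outcomes are seen.

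At stake is a modest amount of precision, and protection of the primary estimate against within-stratum imbalance on its own baseline. The validity of the test is not at stake.

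**Working it through.** **1. The plan's own figures reproduce.** For Exhibit D.8.B with 110 programs per arm and 20 residents per program, SD 9.027, ICC 0.012, two-sided alpha 0.0443 and 80% power:

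(2.011 + 0.842) × 9.027 × √[2 × (1 + 19 × 0.012) / (110 × 20)] = 0.86, as printed.

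From Exhibit D.8.A, the strata cut Level-2 variance by 1 − 1.821/7.413 = 75.4%, as stated in D.8.3. The power basis therefore already rests on quartile strata.

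**2. What the dummies leave behind.** For normally distributed program means, the quartile means lie at ±1.271 and ±0.325 SD. The share of baseline variance between quartiles is (1.271² + 0.325²)/2 = 0.86. About 14% lies within quartiles.

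**3. Can stratum counts explain the D.9 gap?** The gap is 50.48 − 49.98 = 0.50. With 209 programs, near-equal quartiles, a fifth stratum of 0 to 39 programs, even splits within strata and totals of 106/103, unequal counts produce a gap of at most about 0.1 point at SDs of 3.07 to 3.88. Under D.7.3, most of a true 0.50 gap would lie within quartiles.

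**4. Simulation of what would carry through.** Inputs from the SAP are Level-2 and Level-1 variances 7.413 and 83.483 (Exhibit D.8.A) and program sizes of about 19.9, SD 9.6, range 3 to 54 (D.8.1). Assumptions are 8 programs in the fifth stratum, no resident answering at both times, and normal or left-skewed program effects. There were 6,000 trials per shape, fitted with precision weights. The correlation is between 2019 and outcome-year program effects. The slope is the change in the stratum-only estimate per point of baseline gap.

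| Assumed correlation | Slope, normal | Slope, skewed | × 0.50 gap |
|---|---|---|---|
| 0.3 | 0.14 | 0.15 | 0.07–0.08 |
| 0.5 | 0.24 | 0.26 | 0.12–0.13 |
| 0.7 | 0.33 | 0.36 | 0.17–0.18 |
| 0.85 | 0.40 | 0.44 | 0.20–0.22 |
| 1.0 | 0.47 | 0.51 | 0.24–0.26 |

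A separate run gave a slope of 0.09 at 0.3, so the range is rounded to 0.05–0.25. At zero correlation there is no shift. With the continuous mean added, the slope is 0.003 to 0.011 (within about 0.04 of zero in a simpler repeat).

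The standard error runs from 0.477 (correlation 0.3) to 0.393 (1.0), so the detectable difference is 2.853 × SE = 1.36 to 1.12. The shift is then 0.05/1.36 = 4% to 0.25/1.12 = 22% of it. The variance gain from the added covariate is 0 to 8.5%.

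**5. How plausible is the D.9 gap?** A gap of 0.50 or more in either direction occurred in 1.3% (normal) and 1.7% (skewed) of simulated allocations. The SD ratio 3.88/3.07 = 1.26 is also unusual: that or more in either direction occurred in about 0.3% to 1.1% of allocations in a separate simulation. The program types sum to 55 + 46 + 3 = 104 and 52 + 48 + 2 = 102, so 206 against the stated 209.

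**6. Limits.** F.5.2 says that "the first SECOND Trial Resident Survey after dissemination of the Intervention will occur in January 2021", and Section H runs the surveys to January 2023, so outcomes come two to four years after baseline. The SAP has persistence data at one year only. The Stratum 4 minus Stratum 1 coefficient of 6.258, divided by an assumed baseline distance of 2.542 × 3.88 or 2.542 × 3.07, gives 0.63 or 0.80 outcome points per baseline point.

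Without shared residents, the reliability of a program mean is 7.413/(7.413 + 83.483/19.873) = 0.64, so quartiles could remove at most about 0.86 × 0.64 = 55% of Level-2 variance. The observed 75.4% exceeds this, which fits the same residents answering in adjacent years.

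Taken at face value, 75.4% would imply a continuous-score reduction of 0.754/0.861 = 87.7%, leaving a Level-2 variance of 0.91. With 20 residents per program the variance ratio in the strata-only model is (0.91 + 83.721/20)/(1.821 + 83.721/20) = 0.85, a 15% gain. The true figure at the trial's lags could thus lie above or below the simulated range.

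**The case against.** The strongest reply is that this is a preference. Adjusting for the randomization strata matches the design. D.7.2 gives reasons for the number of strata, including limiting model parameters, and the power calculation uses the same strata. The gain is small, and F.3.1.2 does not exclude the continuous score. All of this stands, and it is why the point is an improvement and not a fault. An open list still does not prespecify the covariate. The F.3.1.2 exclusions cover variables that the intervention may affect and structural program measures; a 2019 outcome mean is neither.

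A reader might go further and infer from D.9 that the stratum-only estimate is shifted towards Intervention, the direction of the hypothesis. The documents do not support that. Both the gap and the SD ratio are rare under D.7.3, which suggests that D.9 may not show simple program means of all ranked programs. It does not state its weighting or which programs it includes, and no baseline means by stratum and arm are given. Even a genuine gap would be chance in one allocation, not bias of the method.

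**Conclusion.** It holds as a low-cost improvement. The primary-outcome models name baseline burnout only through strata, although the continuous score is already computed for every program with 2019 data. The planned analysis remains valid.

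The variance gain is 0 to about 9%, assuming no shared residents and an unknown correlation at two to four years. The firmer benefit is protection against within-quartile imbalance, which the continuous mean removes almost entirely in simulation.

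The 0.05 to 0.25 point figure is conditional on D.9 showing simple program means, on alternation as in D.7.3, and on correlations of 0.3 to 1.0. No directional shift should be claimed until D.9 is reconciled.

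**What to change.** 1. Reconcile Exhibit D.9 with the allocation lists. State whether its means are program- or resident-weighted and which programs they include, and explain the 206 against 209.
2. In F.3.1.2, prespecify the continuous 2019 program-mean T-score as a fixed covariate in addition to the randomization strata. Set programs in the fifth stratum to a constant and keep their dummy. Retaining the strata also covers departures from linearity between quartiles.
3. Carry the covariate into the F.3.1.1 and F.3.1.3 models, and add the missing fifth-stratum term to the F.3.1.3 formula.

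The cost is SAP wording and one degree of freedom among about 200 programs. No new data are needed.
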